3.1 Inclusion Criteria

Participants will be: (1) Age 18-55 inclusive; (2) Ability and willingness to give informed consent; (3) Confirmed diagnosis of BD based on DSM-IV criteria being met from previous enrollment in the Prechter Bipolar Longitudinal Study (HUM00000606, PI: [name]); (4) We will select BD patients scoring above published norms (upper 50th percentile) on the NEO-PI impulsivity facet ⁶ to ensure that

the recruited patients exhibit the network dysfunction targeted by the tACS paradigm and therefore have the potential to benefit from this neuromodulation technique. (5) On a stable dose of medication for 2 weeks prior to Sessions 2 & 3.

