4.2 Blinding

Participants, study coordinator and clinical assessor will be blind as to which session the participants receive active or sham treatment. The PI and the data analyst will be aware of the intervention assignment.

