Flanker Task. After completing the Emotion Go-NoGo task, participants will perform a separate cognitive control task (i.e., Flanker task; described below). Accuracy and reaction time will be used to index cognitive control behavior as outcome measures. EEG recorded during the Flanker task will be used to assess neurological indicators of attention control. Participants will then be 50-50 randomized to receive either the Sham treatment first or tACS treatment first at Session 2.

7) Randomization. Subjects will be randomized on a 50-50 basis to receive active vs. sham stimulation. If participants are randomized to the active group at Session 2, they will go to the sham group at Session 3, and vice versa. The participant will not be told which group they were randomized to. The randomization schedule will ensure an equal distribution across the group. Randomization lists

will be generated by random condition generator and will be programmed into the computer that controls the tACS device by the postdoc fellow or PI.

Sessions 2 and 3: Sham vs. Active tACS Session (~2-3 hours)

These sessions will occur at the University of Michigan Rachel Upjohn Building. Participants will undergo two sessions, separated by ~ 1 week. Procedures will be identical for each session.

- 1) *Pre-Visit Preparations*. Research staff will contact the participant to remind them about the study visit and to ask if they have had any medication changes since their last visit. If yes, the participant will be re-scheduled for an appointment time in which the criteria for a stable dose of at least two weeks has been achieved. Additionally, participants will also be asked if they have had any recreational drug use since their last study visit. If yes, the participant will have to be re-scheduled 30 days out.
- 2) *Arrival on scheduled session day*. Participants will arrive at the Rachel Upjohn Building where they will be greeted by a member of research staff and escorted to the treatment room. Pregnancy urine test will be given if participant opted out of signing the Pregnancy Attestation Form.
- 3) *Clinician Administered Assessments*. In-person clinical assessments will be completed by a trained member of staff. All study clinicians are blinded to the treatment arm.

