7.0 STATISTICAL CONSIDERATIONS

Aim 1 - Acceptability and Tolerability. Neuromodulation studies typically use dropout rate and reported adverse events as measures of acceptability and tolerability, respectively.¹² We will compare the percentage of participants requesting to discontinue the session and the severity of side effects reported following the tACS vs. sham procedure using Bayes factors (BF).

Aim 2 - tACS Effects on Neural Synchrony and Cognitive Control Behavior. EEG data preprocessing and spectral analyses will be conducted using custom MATLAB scripts and EEGLAB following the general methods described in **PI [name]**'s published work.⁷ Briefly, data will be downsampled to 500 Hz, filtered (0.1 – 100 Hz), re-referenced to common average, segmented into short epochs (for task data, -400 to 1800 ms time-locked to onset of stimuli; for rest data, 2 s epochs), applied independent component analysis to reject non-neural artifacts, baseline adjusted, followed by automatic artifact rejection of epochs containing voltage exceeding ±100 μ V. Data will be mirrored on both ends to minimize edge artifacts, applied Morlet wavelet convolution to extract power of different frequencies from 2 to 60 Hz. Theta-gamma PAC will be computed using the Kullback-Leibler Modulation Index (KLMI)⁸ implemented in the PAC Tools plugin for EEGLAB.⁹ Neural synchrony (theta-gamma PAC) during the rest EEG blocks and cognitive control performance (sensitivity d', response bias β , and reaction time on the Emotion Go-NoGo task) will be analyzed in separate repeated-measures ANCOVAs, with stimulation (tACS, sham) as within-subjects factor.

Potential Problems & Alternative Strategies

Participants Dropout. The study design entails each participant completing all 3 sessions. Our experience of conducting multiple-session neuromodulation studies suggests that average dropout rate for each subsequent session is 10-15%. We will enroll 30 participants to ensure that at least 20 participants will complete the study even with an overall dropout of 30%.

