8.2 Roles & responsibilities for regular operations

*PI*: The PI will meet with study staff on a weekly basis to monitor the progress of the study. During phases when subject recruitment is occurring, the PI will review screenings and scheduling of assessments, as well as strategies to improve recruitment yield at weekly meetings with the study team. Issues such as maintaining confidentiality and privacy of participants during screening,

assessment and data collection, protocol deviations and adverse events will be reviewed. For serious adverse events, the PI will be notified as soon as the SAE comes to the attention of study staff.

Study coordinator/research assistant: This bachelors level individual will carry out the screening and informed consent, and they will provide additional study information, all under the supervision of the PI. The individual will be trained in screening, administering consent and information to the participants. Questions about eligibility will be discussed with the PI. This individual will administer surveys and neuropsychological tests, monitor the participants during the procedure and administer the tACS stimulation. They will receive training in the administration of tACS to ensure they can safely operate the device and are aware of potential side effects. They will conduct any necessary follow-up safety reviews.

*Clinical Assessor:* Screenings will include thorough assessment of psychiatric health by a masterslevel clinician with experience in administration of psychiatric interviews. They will ensure the absence of any neuropsychiatric conditions in the subjects, as well as health conditions that would be a contra-indication to TMS or MRI procedures.

8.3 Frequency and type of other study monitoring:

Institutional Review Board monitoring: Approval of all procedures, advertisements and materials given to subjects will be secured from the University of Michigan IRBMED. Annual reviews will be conducted by IRBMED, including the number of subjects screened, enrolled and withdrawn. The IRB will also review protocol deviations, adverse events (according to the reporting timetable of IRBMED) and complaints that arise in connection with the study.

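### Randomising at the end of Session 1, before the Session 2 checks, lets a PI who knows the sequence make pre-stimulation decisions and leaves sequence balance unassured; a minor point, cheaply fixed

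*Combined protocol and SAP*

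**What the plan says.** **Timing.** Section 5.2, under the Session 1 Flanker Task, states: "Participants will then be 50-50 randomized to receive either the Sham treatment first or tACS treatment first at Session 2". The numbered Randomization step that follows is also a Session 1 step, and the Time and Events Table (Section 5.4) marks Randomization only under Session 1.

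**Balance and custody.** The same step says "Subjects will be randomized on a 50-50 basis to receive active vs. sham stimulation" and "The randomization schedule will ensure an equal distribution across the group". It names a random condition generator but no blocks. The lists "will be programmed into the computer that controls the tACS device by the postdoc fellow or PI".

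**Checks that come later.** Inclusion criterion 5 in Section 3.1 reads "On a stable dose of medication for 2 weeks prior to Sessions 2 & 3". Section 5.2 asks about medication changes and recreational drug use at the contact before each stimulation session. The pregnancy test or attestation, the urine screen if indicated and the C-SSRS recur at Sessions 2 and 3 (Section 5.4). Section 10.2 expects about 1 week between the initial assessment and the tACS sessions, possibly about 30 days for some.

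**Who knows and who decides.** Section 4.2 says "The PI and the data analyst will be aware of the intervention assignment"; participants, coordinator and clinical assessor are blind. Section 5.2 gives the PI discretion over a second chance after a positive urine screen, and its Stopping Rules let the investigator withdraw subjects. Section 8.2 adds "Questions about eligibility will be discussed with the PI".

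**Dropout.** Section 7.0 says the "average dropout rate for each subsequent session is 10-15" per cent, without giving causes. It enrols 30 so that at least 20 complete even with 30% overall dropout.

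**The concern.** Nothing done in Session 1 uses the allocation, so allocating there gains nothing and opens a gap between allocation and first stimulation. Two things follow.

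First, discretionary decisions in that gap are made after allocation, and one person entitled to make them may know the sequence. Sound ordering puts the eligibility decision before the allocation is known.

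Second, people who leave during the gap have been allocated but contribute nothing to the tACS-sham comparison or to tolerability. The schedule can be balanced while the people stimulated are not. Section 7.0 names stimulation as the only within-subjects factor, with no period or sequence term, and the same task is repeated in both sessions. Any sequence imbalance would therefore let a fraction of a Session 2-to-3 practice effect into the contrast. Section 7.0 also does not say how people randomised but never stimulated are counted.

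**Working it through.** **Inputs.** 30 enrolled; dropout d = 10-15% per subsequent session; 30% overall; N = 20, f = 0.21, within-subject correlation ρ = 0.8, alpha 0.05 (all Section 7.0). Assumptions: all 30 enrolled are randomised, 15:15; the first 10-15% falls between Sessions 1 and 2; loss is unrelated to sequence.

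**1. The plan's own figures.**
- Power: noncentrality f²·N·m/(1−ρ) with m = 2 conditions is 0.21² × 20 × 2 / 0.2 = 8.82 on (1, 19) df, giving 0.804. The stated 80% reproduces.
- Retention: 30 × 0.70 = 21, so at least 20 holds. Compounding two losses gives 30 × 0.90² = 24.3 or 30 × 0.85² = 21.7.

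**2. Randomised but never stimulated.** 30 × 0.10 = 3.0; 30 × 0.15 = 4.5.

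**3. Balance under the current plan.** The two sequence counts are independent Binomial(15, p), with p = 1−d at Session 2 and p = (1−d)² for completers.

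| | d = 10% | d = 15% |
|---|---|---|
| Session 2: expected difference | 1.26 | 1.52 |
| Session 2: P(equal) | 0.25 | 0.21 |
| Session 2: P(difference ≥ 3) | 0.12 | 0.19 |
| Completers: expected difference | 1.68 | 1.93 |
| Completers: P(difference ≥ 3) | 0.24 | 0.31 |

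**4. Allocating at Session 2 instead.** Simulation, 200,000 replicates: the list is used in order by those who attend Session 2, then d is lost again before Session 3. Cells show P(difference ≥ 3) for d = 10% / 15%.

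| List | Session 2 | Completers |
|---|---|---|
| Unblocked 15:15 list of 30 | 0.12 / 0.19 | 0.24 / 0.31 |
| Blocks of 2 | 0 / 0 | 0.13 / 0.18 |
| Blocks of 4 | 0 / 0 | 0.15 / 0.20 |

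Stopping an unblocked list after about 25.5-27 of its 30 slots unbalances it exactly as random loss does, so moving the step without blocking gains no balance. With blocks of 2 or 4, the Session 2 difference cannot exceed 2.

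**5. Size of the leak.** The fraction of a period effect entering an unadjusted contrast is (n₁−n₂)/N. Its root mean square among completers is 0.092 / 0.118 now and 0.072 / 0.092 with blocks of 2 at Session 2.

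**6. Power.** Completers stay at 24.3 / 21.7 whichever session randomises. In a period-adjusted analysis at N = 20 (18 df), noncentrality is multiplied by 1 − (difference/20)². Power is 0.802 at 10:10, 0.798 at 11:9, 0.786 at 12:8 and 0.764 at 13:7.

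**The case against.** The strongest reply is that little is at stake.

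- **The checks mostly delay.** Medication change and drug use lead to rescheduling, not exclusion. Only a positive pregnancy test, a urine-screen outcome or investigator withdrawal could remove someone, and no rate is given. A reader might infer that the checks cause the loss of 3 to 4.5 people; the documents do not support that. This stands.
- **Balance is promised for the schedule, not for attendees.** A reader might infer that the promised balance is lost. It is not: it holds among those randomised, and among those stimulated the difference is below 3 with probability 0.81-0.88. This stands; the accurate statement is that balance is not assured.
- **The leak is small.** Suppose, for illustration, a period effect as large as the planned detectable effect, 2f = 0.42 SD. The blocked fix then reduces the leak by (0.020 to 0.026) × 0.42, about 0.01 SD, against a standard error of √(2 × 0.2/20) = 0.14 SD. A period term would remove the leak at any imbalance. This stands, and that is a separate matter.
- **Concealment.** A reader might infer that allocation concealment is defeated. That goes too far. The Section 8.2 sentence on eligibility questions sits in the description of screening and consent; the Session 2 questions are rule-based and asked by research staff; coordinator and assessor are blind; everyone is assigned both conditions. No allocation-dependent loss is shown. What remains is that the PI has discretion in Section 5.2 and knows the assignment under Section 4.2.
- **Criterion 5 also covers Session 3**, which no randomisation time can follow. True, but its Session 2 part can precede allocation.
- **The list sits in the device computer**, so a slot may in practice be used only at Session 2. The text does not settle this; if so, the change makes the text match practice.

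**Conclusion.** The ordering problem is in the text, and it is minor. Randomisation precedes the Session 2 checks, so a discretionary decision before stimulation can be made by someone who knows the sequence. That opening, closed at almost no cost, is the main reason to act. Imbalance is secondary: an expected 1 to 2 people, with probability 0.12-0.19 of 3 or more at Session 2.

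A reader might infer that power or the completer target suffers. Neither does: the 30% allowance already covers these losses, and later randomisation does not get more people stimulated. Loss between Sessions 2 and 3 can still unbalance the sequences after the change.

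The figures rest on 30 randomised 15:15, dropout of 10-15% at each step, and loss independent of sequence. The plan does not say whether Session 1 screen failures count within the 30. If they do, fewer than 30 are randomised and the 3 to 4.5 shrinks in proportion.

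**What to change.** 1. Move the Randomization step in Section 5.2, the sentence on it in the Session 1 Flanker paragraph, and the X in the Time and Events Table to Session 2. Take the next slot after that day's existing checks are recorded and before the device is set.
2. Generate the list in small permuted blocks, for example sizes 2 and 4 mixed at random. Withhold the block sizes from the PI, since someone who knows past allocations can sometimes infer the last slot of a block.
3. Have the postdoc fellow, already named as an option, hold and program the list, so that the PI does not know the next allocation before Session 2. Align Section 4.2 accordingly.

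Cost: a few sentences, one table cell and a regenerated list. The downside is that the postdoc fellow must load the allocation on the day. The gain is allocation after the Session 2 checks, no one randomised and then lost before Session 2, and P(difference ≥ 3) reduced to 0 at Session 2 and to about 0.13-0.20 among completers.

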- 3) Urine Drug Screening (UDS). Participants who screened positive for current substance use disorder will be administered a UDS. If their UDS indicates the presence of a substance, they will not undergo that day's visit. At the PI's discretion, the participant may be given the option to abstain from all substance use and be rescheduled to provide another urine sample. If they have a clean UDS at that time, they will be able to continue with the visit at that time. Those that are not given the option or who refuse to do the UDS will be a screen fail. Participants who have no active current substance use will not be required to provide a urine sample.
- 4) *Self-Rated Assessments*. Participants deemed eligible will complete self-rated assessments and computerized tasks through Qualtrics, using an anonymous survey link. No identifiable information will be collected within the survey.
- 5) *Baseline EEG*. EEG will be recorded using a 64-channel electrode cap using EEG procedures that are standard in cognitive ERP and time-frequency analysis research. The cap is an elastic cap that fits snugly over the scalp of the participant, holding the electrodes in place. A standard conductive electrode gel will be inserted into each electrode using a blunt-needle syringe. The scalp will be gently rubbed with a swab to improve electrode impedance (i.e., to lower the electrical resistance). Typical application time for an electrode cap lasts around 30 minutes. The electrode for monitoring eye movements will be affixed with adhesive collars. The skin will also be cleaned with an alcohol swab for this electrode. The cap and electrodes will be disinfected after each use with a disinfectant recommended by BrainVision Company (e.g., Cavicide). Other items will be disposed of after each use. The experimenter will wipe the residual electrode gel from the participant's hair and skin after the EEG session.

Emotion Go-NoGo Task. Participants will undergo an EEG and perform a cognitive control task (Emotion Go-NoGo task; described below).

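### No allocation concealment is described, the PI may load the randomisation list and knows assignments, and the PI also influences entry before randomisation; the likely effect is small and the fix is cheap

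*Combined protocol and SAP*

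**What the plan says.** **Access to the list.** Section 5.2, Session 1, item 7 says that lists come from a random condition generator, give equal numbers per sequence, and "will be programmed into the computer that controls the tACS device by the postdoc fellow or PI".

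**Who is blind.** Section 4.2: "Participants, study coordinator and clinical assessor will be blind as to which session the participants receive active or sham treatment". It continues: "The PI and the data analyst will be aware of the intervention assignment". The postdoc fellow is not mentioned there.

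**Influence on entry.** After a positive urine drug screen, Section 5.2 item 3 says: "At the PI's discretion, the participant may be given the option to abstain from all substance use and be rescheduled to provide another urine sample". It adds: "Those that are not given the option or who refuse to do the UDS will be a screen fail". Section 8.2 says "Questions about eligibility will be discussed with the PI" and has the PI review screenings and scheduling each week.

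**Order of events.** Randomisation closes Session 1, after these decisions: "Participants will then be 50-50 randomized to receive either the Sham treatment first or tACS treatment first at Session 2".

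**What is not there.** No section names an independent holder of the list, coded or sealed allocations, a rule that a sequence is released only once eligibility is recorded, or a block size.

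**The concern.** Concealment means that nobody who can affect whether or when a person enters knows, or can guess, what that person will be allocated. It is a separate matter from blinding after allocation. Here one role may handle the list, is aware of assignments, and has a say in entry. Even if the postdoc fellow does the loading, someone who knows past assignments under a schedule forced to balance can partly predict the next one, and can predict it with certainty once one sequence is full.

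In this cross-over only the order is allocated, so less is at stake than in a parallel-group trial. Two routes to bias remain:

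- **Withdrawal (primary outcome 2).** A person who leaves after Session 2 has received only one condition. If people more likely to leave were gathered in one sequence, part of the tACS-versus-sham comparison would be between different kinds of people.
- **Period or practice effects (Aim 2).** If the two sequence groups improve by different amounts between Sessions 2 and 3, that difference enters the stimulation contrast.

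**Working it through.** **Step 1. The plan's own figures.** Section 7.0 gives N = 20, f = 0.21, correlation 0.8, alpha .05 and 80% power. With two conditions, λ = f² × n × 2/(1 − ρ) = 0.0441 × 20 × 2/0.2 = 8.82 on 1 and 19 degrees of freedom, which gives 80.4%. Enrolment also agrees: 30 × 0.70 = 21 completers, against the 20 needed. Both figures reproduce, and neither depends on concealment.

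**Step 2. Withdrawal.** The number of participants reaching the PI's discretion is not given, so every input but the first two is an assumption.

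- 30 enrolled, 15 per sequence (from the plan).
- 10% withdrawal per stimulation session for ordinary participants (low end of the plan's 10-15% per session).
- 4 borderline participants at 40%, all placed sham-first; no true effect of tACS.
- The same risks in Sessions 2 and 3; the denominator is those starting each session.

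| | Start Session 2 | Withdraw | Start Session 3 | Withdraw |
|---|---|---|---|---|
| Sham-first (4 borderline, 11 ordinary) | 15 (sham) | 1.6 + 1.1 = 2.70 | 2.4 + 9.9 = 12.3 (tACS) | 0.96 + 0.99 = 1.95 |
| tACS-first (15 ordinary) | 15 (tACS) | 1.50 | 13.5 (sham) | 1.35 |

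- Sham: (2.70 + 1.35)/(15 + 13.5) = 4.05/28.5 = 14.2%
- tACS: (1.50 + 1.95)/(15 + 12.3) = 3.45/27.3 = 12.6%
- Spurious difference: about 1.6 points.

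Varying the inputs:

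| Scenario | Sham | tACS | Difference |
|---|---|---|---|
| 6 borderline, same risks in both sessions | 4.65/28.5 = 16.3% | 3.75/26.7 = 14.0% | 2.3 points |
| 4 borderline, Session 3 risks halved | 3.375/28.5 = 11.8% | 2.475/27.3 = 9.1% | 2.8 points |
| 6 borderline, Session 3 risks halved | 3.975/28.5 = 13.9% | 2.625/26.7 = 9.8% | 4.1 points |
| 4 borderline, Session 2 only | 2.70/15 = 18.0% | 1.50/15 = 10.0% | 8.0 points |

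With both sessions at equal risk, 2 to 6 borderline participants and withdrawal of 25-40%, the difference runs from 0.3 to 2.3 points if all are sham-first, and from 0.1 to 1.1 points if 75% are.

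**Step 3. Aim 2.** A stable difference in level between sequence groups gives no bias. With groups 1 SD apart, simulation gave a mean bias of about 0 and a type I error of 4.7%. A practice effect that differs by δ between sequences gives a bias of δ/2. The SD of the paired difference is √(2 × (1 − 0.8)) = 0.632 outcome SD. With n = 20:

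| δ (SD) | Bias (SD) | Two-sided type I error |
|---|---|---|
| 0 | 0 | 5.0% |
| 0.1 | 0.05 | 6.3% |
| 0.2 | 0.10 | 10.3% |
| 0.3 | 0.15 | 17.2% |

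The documents give no value for δ. If only 4 of 15 in one sequence are affected, a group difference of 0.1 SD needs those 4 to differ from the rest by 0.1 × 15/4 = 0.375 SD in practice effect. A period term would not remove this bias: with equal sequences the period-adjusted estimate, half the difference between sequences in the Session 2 to 3 change, also carries δ/2.

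**The case against.** Much of the opposing case stands.

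- A reader might infer that the PI sees the next entry before deciding who enters. The documents do not say so. Section 4.2 speaks of awareness of assignment, Section 5.2 allows either of two people to load the list, and advance sight is inferred from the absence of any concealment step.
- A reader might infer that rescheduling moves a person to a later place on the list. Nothing says whether entries are used in order of randomisation or tied to participant identifiers.
- The PI's role in entry is narrow. Under Sections 4.2 and 8.2, screening and psychiatric assessment are done by a blinded coordinator and a blinded assessor. The one explicit discretion is the repeat urine screen, and continuing then needs a clean result. The pool cannot be sized: Sections 5.1 and 5.2 describe different groups being sent for the screen, Section 3.2 criterion 3 bears on the same people, and these passages must be reconciled.
- A reader might infer a withdrawal bias of 8 points or more from the Session 2 figures. That counts half of the cross-over. Primary outcome 2 covers the stimulation session in either condition, and borderline participants who stay go on to receive tACS, where their withdrawals count against tACS. Even 8 points is 1.2 people of 15, below the standard error of a 15-versus-15 difference at 10%: √(2 × 0.1 × 0.9/15) = 0.11.
- The direction of any steering is conjecture. The plan discloses who is unblinded and never claims concealed allocation.

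What remains is that the roles as written permit the problem and no safeguard is stated. Blinding the coordinator and assessor does not cover cases that reach the PI.

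**Conclusion.** The point holds as a minor one. The PI may load the list, is aware of assignments, and influences some entry decisions before randomisation; concealment is not described. That makes foreknowledge or partial prediction possible. It does not show that either occurs.

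The exposure is confined to order-related withdrawal and to practice or period effects that differ between sequences. The size is unknown and probably small: about 1.6 points of withdrawal in the worked case and at most about 2.3 with 6 borderline participants, assuming equal risks in both stimulation sessions. It is larger only if withdrawal in Session 3 is rarer, or if Session 2 alone is analysed, which the plan does not specify. For Aim 2, a material effect needs a sizeable practice difference in the few people affected. Sample size and power are untouched.

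**What to change.** - **Section 5.2, item 7:** remove the PI as a permitted loader. State that the list is generated and loaded as coded conditions by the postdoc fellow, or another existing team member, who has no role in screening, eligibility or rescheduling. The documents do not describe the postdoc's duties, so this should be confirmed.
- **Section 4.2:** replace, rather than supplement, the statement that the PI is aware of assignment. The new text should say that the PI has no access to the list or to assignments until enrolment is complete, except through Section 6.6.
- **Either section:** state that eligibility, and any reschedule or screen-failure decision, is recorded before each sequence is released.

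The cost is a short amendment, with no added staff, procedures or participants. The downside is that the PI cannot cover list loading when the loader is absent and must use Section 6.6 to see an assignment. Concealment cannot be restored for people already randomised, so the change is worth making before the next one.
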